CNR1 (the gene for CB1 receptor) has 2 synonymous single nucleotide polymorphisms (SNPs), rs35057475 and rs1049353; neither results in a change in amino acid sequence. There is an (AAT) n repeat at the 3' end of CNR1, 18,000 bases downstream from the start site of exon 4 of CNR1. The number of repeats is highly variable (from 2 to 6 repeats) and, although associations with psychiatric disease, i.v. drug use, and response to antipsychotics have been described (58-62), the functional significance of this genetic variation is unclear. The T allele of **CNR1 polymorphism rs806378** is associated with altered nuclear protein binding in an electrophoretic mobility shift assay, suggesting that rs806378 is a **functional** polymorphism (63). We previously demonstrated **association of this genotype** with gastric and colonic functions (see Background).

FAAH 385C to A allelic variant (rs324420) leads to a Pro129Thr amino acid sequence change, which decreases expression of the FAAH protein due to reduced protein stability (64). The prevalence of the A allele is 16%–25% in studies of Caucasians in the NCBI database. Our laboratory has previously confirmed the A allele frequency to be 25% in our sample population of healthy controls and IBS patients in southeastern Minnesota (18). Reduction in FAAH protein level and activity compromises inactivation of the endocannabinoid anandamide, which leads to higher synaptic concentrations of anandamide and resulted in a greater effect of the exogenously administered cannabinoid agent, dronabinol, via activation of CB1 and CB2 receptors.

In addition, we shall screen patients' **CYP3A4** and **CYP2C19** genes, which impact the main CYP450 enzymes responsible for cannabidiol metabolism (65). Ultra-rapid metabolizers for CYP2C19 [estimated 17% and 18% based on literature review (36)] will be excluded since this could impact assessment of effects of cannabidiol.

General Approach for Statistical Analyses

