- Abdominal pain score on NDI in functional dyspepsia (aim 1b)
- Proportion of responders based on adequate relief in functional dyspepsia (aim 1b)
- Average daily aggregate symptom score for upper abdominal pain, nausea, bloating, fullness, and early satiety (each on a scale of 0 to 3) in functional dyspepsia (aim 1b)

LPDS score and FDSD scores will be exploratory endpoints since they have only recently been validated.

Sample Size Assessment

This is based on results of the primary endpoints in our Mayo Clinic lab. Expected (80% power, $\alpha=0.05$, assuming parallel-group study and unpaired analysis with $n=22$ in aim 1a and **n=24 aim 1b**) demonstrable differences compared to placebo show that the study is powered to detect clinically relevant effects of cannabidiol based on the variation (SD) observed from our Mayo prior studies (42-44,46,47).

TABLE 3. Sample Size Assessment: Response	Mean	SD	Effect size detectable (absolute [% of mean], $n=24$ per group)
Fasting gastric volume, mL	273	57	47mL (17%)
Postprandial gastric volume, mL	848	111	91.7mL (10.8%)
Gastric emptying of solids $T_{1/2}$, min	122	29.8	24.62 (20.2%)
Volume to fullness, mL	755	330	273mL (36.2%)
Maximum tolerated volume, mL	1283	400	330.5mL (25.8%)
Δ from baseline in average (of 3 subscales in) GCSI-DD	-1.4	0.5	0.413 (29.5%)
Average Aggregate Symptoms Score for dyspepsia	1.42	0.64	0.50 (35.2%)
NDI overall quality of life score	63.6	22.5	18.6 (29.2%)
NDI abdominal pain score	29.4	10.4	8.6 (29.3%)
NDI postprandial distress score	12.8	7.5	6.2 (48.4%)

Therefore, the study has sufficient power to detect clinically relevant effects on quantitative traits. The study will provide important information on the mean response in clinically important endpoints in the two trials and, therefore, provide important preliminary information, such as coefficient of variation of the response in the current hypothesis-generating trials in order to plan future hypothesis-testing trials.

Interim Analysis: As part of an on-going method to compare the effects of each medication tested and placebo, an interim analysis will be conducted when 50% of the first specific aim has been reached.

Rationale for Interim Analysis:

- To assess power of the study based on the actual coefficient of variation as measured in the actual study with >50% completed; this is because the coefficient of variation could be different from the COV used in the a priori power calculation used in development of the protocol.

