b. **Consideration of sex as a biological variable:** In the ~1270 person database, 60% were female (37). We anticipate a female to male ratio of 1.5:1 to ensure we can assess sex as a biological variable.

c. Scientific premise for inclusion of both genders includes: Although functional dyspepsia is more prevalent in females, there is no a priori evidence that the effect of cannabidiol differs between genders, and the pathophysiological mechanisms do not appear to be different between genders. Therefore, our study will assess treatment efficacy in **both genders, and we shall recruit ~ equal numbers of men and women.**

d. Drop-outs and missing data will be managed as for specific aim 1a.

Significance: This study will evaluate efficacy, safety, and mechanisms of action of cannabidiol in the largest single-center study in functional dyspepsia to date, and it will provide information on the coefficient of variation in patient reported outcomes to plan future hypothesis-testing, multicenter studies of the effects of cannabidiol in patients with functional dyspepsia.

Aim 2: Treatment by genotype interaction of cannabidiol and *FAAH* and *CNR1* genes and gastric functions in patients with functional dyspepsia or gastroparesis

Hypothesis 2: *FAAH* rs324420 and *CNR1* rs806378 genotype significantly affect the response of gastric accommodation, gastric emptying and satiation to treatment with cannabidiol in patients with gastroparesis or functional dyspepsia with normal baseline gastric emptying.

Specific Aim 2: To assess pharmacogenetics effects of variants in *FAAH* and *CNR1* genes on the pharmacodynamics effects of cannabidiol vs. placebo on gastric accommodation, gastric emptying and satiation in the same patients with gastroparesis or functional dyspepsia.

Rationale: In prior studies, *FAAH* rs324420 and *CNR1* rs806378 gene variants were associated with gene by treatment interactions on diverse gastrointestinal motor functions in response to the non-selective cannabinoid agonist DRO (see background). Genotype distributions (18,19) in participants in prior Mayo Clinic studies are shown in Figures 11 and 12. We have previously demonstrated

(18,19) the MAFs of the *FAAH* and *CNR1* variants in our catchment population are consistent with NCBI and other literature reports with *FAAH* MAF of 0.25 and *CNR1* MAF of 0.29.

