Experimental design: From specific aim 1, there will be 46 patients (22 with gastroparesis and 24 with functional dyspepsia) treated with cannabidiol; we shall compare in these patients the association of gene variants on the effects of cannabidiol on gastric emptying using a dominant genetic model. The model will include cannabidiol, gene variants, plus the

[figure not shown]

Figure 11: *FAAH* rs324420 genotype distribution in FGID and healthy controls studied at Mayo Clinic and reported distribution in NCBI and in a study mostly in Caucasians.

[figure not shown]

Figure 12: *CNR1* rs806378 genotype distribution in FGID and healthy controls at Mayo Clinic (mostly Caucasians)

include gender, treatment (yes/no) interaction gene x treatment.

Experimental procedures and measurements: All participants will have undergone gastric emptying of solids, gastric volume (fasting and postprandial) and satiation test in specific aim 1. Genotyping for *FAAH* rs324420 and *CNR1* rs806378 and *CYP 3A4* and *2C19* will be performed. See common methods section.

Endpoints: (a) Gastric emptying $T_{1/2}$ solids; (b) Accommodation gastric volume; (c) Satiation by the MTV

Statistical considerations and analysis:

Applying the dominant genetic model, we anticipate there will be a 60:40 split of *FAAH* rs 324420 CC vs. CA/AA, and a 50:50 split for *CNR1*rs806378 CC vs. CT/TT.

Given there will be 46 participants receiving cannabidiol and assuming an approximate 50:50 split of the participants based on both genotypes (that is, 23 patients CC vs. 23 CA/AA *FAAH* rs 324420 or 23 CC vs. 23 CT/TT for *CNR1* rs806378), we anticipate the following effect sizes attributable to the gene variants (Table 4):

Table 4. Response	Mean	SD	Effect size detectable ([% of mean], n=24/ genotype group)
Fasting gastric volume, mL	273	57	47mL (17%)
Postprandial gastric volume, mL	848	111	91.7mL (10.8%)
Gastric emptying solids $T_{1/2}$, min	122	29.8	24.62 (20.2%)
Volume to fullness, mL	755	330	273mL (36.2%)
Maximum tolerated volume, mL	1283	400	330.5mL (25.8%)

ANCOVA will compare the genotypes for each gene variant, including baseline GE $T_{1/2}$ as covariate.

Anticipated results: Effect of cannabidiol will be significantly associated with *FAAH* and *CNR1* genotypes consistent with the hypothesis that the gene variants impact the function of the receptor target or the inactivation of endocannabinoids that modulate gastric motor functions, or calorie intake at satiation test.

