Potential pitfalls, precautions taken, and alternative strategies:

Feasibility: The study participants will be enrolled in specific aim 1; the power calculation based on our patient community gene minor allele frequency shows that the study has sufficient power to detect clinically relevant gene * treatment interactions.

Genetic variation in metabolism (inactivation) of cannabidiol: Ultra-rapid metabolizers for *CYP2C19* [estimated 17% and 18% based on literature review (36)] will be excluded since this could impact assessment of effects of cannabidiol.

Consideration of sex as a biological variable: In the ~1270 person database, 60% were female (37). We anticipate a female to male ratio of 1.5:1 to ensure we can assess sex as a biological variable.

Scientific premise for inclusion of both genders includes: Although functional dyspepsia is more prevalent in females, there is no a priori evidence that the effect of cannabidiol differs between genders, and the pathophysiological mechanisms do not appear to be different between genders. Therefore, our study will assess treatment efficacy in **both genders, and we shall recruit men and women in the ratio 1:1.5**.

Drop-outs and missing data will be managed as for specific aim 1.

Significance: This study will evaluate impact of common functional genetic variants in CB1 receptor and cannabinoid inactivation on the pharmacodynamics responses to cannabidiol, potentially important in individualizing therapy with cannabidiol in the treatment of gastroparesis and functional dyspepsia that may impact plan and design of future hypothesis-testing, multicenter studies of the effects of cannabidiol in patients.

Overall Significance of Application: The proposed studies provide the ability to validate a recently approved pharmaceutical grade cannabidiol for the treatment and addressing the unmet need of millions of American citizens with gastroparesis or functional dyspepsia, including personalization of treatment based on genotype by treatment interactions. This research team is uniquely poised to deliver on this vision.

Time Table: **Years 1-4:** specific aims 1, 2; **Year 5:** data analysis and publications

LITERATURE CITED

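### Table 4 gives one set of detectable differences for both genes, sized for 24 per genotype group; with 46 treated patients and the predicted FAAH split, unadjusted power is about 78% for CNR1 and 76% for FAAH

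*Combined protocol and SAP*

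**What the plan says.** The Aim 2 experimental design states that "there will be 46 patients (22 with gastroparesis and 24 with functional dyspepsia) treated with cannabidiol". Under Statistical considerations and analysis, for a dominant genetic model, it says "we anticipate there will be a 60:40 split of *FAAH* rs 324420 CC vs. CA/AA" and expects an equal split for CNR1. The next sentence works from those 46 patients, "assuming an approximate 50:50 split of the participants based on both genotypes", and spells this out as 23 against 23 for each gene.

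Table 4 then lists one detectable difference per response for both genes, headed 24 per genotype group. The five figures are the same as those for these responses in Table 3 (Sample Size Assessment), where the heading is 24 per treatment group. The basis given there is 80% power and alpha 0.05, "assuming parallel-group study and unpaired analysis".

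The Aim 2 rationale reports "FAAH* MAF of 0.25 and *CNR1* MAF of 0.29" for the catchment population. The Aim 2 feasibility paragraph says that "the power calculation based on our patient community gene minor allele frequency shows" sufficient power for clinically relevant effects.

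**The concern.** Two inputs to Table 4 disagree with the text around it. Two groups of 24 make 48 patients, and 46 are treated. An equal FAAH split also contradicts the 60:40 split predicted one sentence earlier. Both errors act in the same direction: fewer patients or less balance gives a larger standard error, so the printed differences are somewhat too small for the stated power. The group-size error affects both genes; the split affects FAAH only.

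FAAH and CNR1 are the only two genes tested for an effect on response in Aim 2. A null result for either would be read against Table 4, so the table should describe the groups that the plan expects to have.

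**Working it through.** **Inputs.** SDs from Table 4: fasting volume 57 mL, postprandial volume 111 mL, gastric emptying half-time (GE T1/2) 29.8 min, volume to fullness (VTF) 330 mL, maximum tolerated volume (MTV) 400 mL. Power 80% and alpha 0.05 come from the Sample Size Assessment; Table 4 restates neither. A two-sided test is my assumption, and it reproduces the table. Group sizes: 46 × 0.60 = 27.6 and 46 × 0.40 = 18.4, so about 28:18 for FAAH; 23:23 for CNR1.

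**Formula.** For a two-sample t-test, the detectable difference δ solves P(|T| > t(0.975, n1+n2−2)) = 0.80. T is noncentral t with noncentrality (δ/SD) × √(n1·n2/(n1+n2)).

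**Step 1: reproduce Table 4.** At 24:24, δ = 0.826 SD. This gives 47.1 mL, 91.7 mL, 24.62 min, 272.6 mL and 330.5 mL, against 47, 91.7, 24.62, 273 and 330.5 printed.

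**Step 2: use the expected groups.**

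| Response | Printed | CNR1, 23:23 (0.845 SD) | FAAH, 28:18 (0.865 SD) |
|---|---|---|---|
| Fasting volume, mL | 47 | 48.2 | 49.3 |
| Postprandial volume, mL | 91.7 | 93.8 | 96.1 |
| GE T1/2, min | 24.62 | 25.2 | 25.8 |
| VTF, mL | 273 | 279 | 286 |
| MTV, mL | 330.5 | 338 | 346 |
| Power at the printed GE T1/2 difference | 80.0% (at 24:24) | 78.2% | 76.3% |

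Across the five rows, power at the printed difference is 78.1 to 78.3% at 23:23 and 76.1 to 76.4% at 28:18.

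**Step 3: separate the causes for FAAH.** Going from 24:24 to 23:23 costs 1.8 points (80.0 to 78.2). Going from 23:23 to 28:18 costs 2.0 points (78.2 to 76.3, before rounding). In detectable difference the steps are 0.8447/0.8261 = 1.023 and 0.8654/0.8447 = 1.024, together 1.048. Equivalently, 28:18 carries the information of 2 × 28 × 18/46 = 21.9 patients per group.

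**Step 4: try the other formula.** The normal approximation is δ = (1.960 + 0.842) × SD × √(1/n1 + 1/n2). At 23:23 this is 2.802 × 0.2949 = 0.826 SD, which also reproduces Table 4. At 28:18 it is 2.802 × 0.3021 = 0.846 SD, or 25.2 min for GE T1/2, with 78.1% power at the printed 24.62. On this reading CNR1 keeps 80%, and only the split matters.

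**Step 5: check the split against the allele frequencies.** Assuming Hardy-Weinberg proportions, the CC share is (1 − q)². For CNR1, 0.71² = 0.504, or 23.2 of 46. For FAAH, 0.75² = 0.5625, or 25.9 of 46, about 26:20. Power at 26:20 on the t-test is 77.5%, which is 0.7 points below 23:23.

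**The case against.** The strongest reply is that the effect is too small to matter. The split alone costs about 2 points of power under either formula, no sample size or decision rule changes, and the Sample Size Assessment calls these trials hypothesis-generating. That is right, and it limits this point to a minor correction.

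The documents name no formula for Table 4. The t-test at 24:24 fits the table's own label and its match with Table 3; the normal approximation at 23:23 fits the text. The 76% is therefore not the only supportable figure. FAAH is below 80% on both.

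The planned analysis is an ANCOVA with baseline GE T1/2 as covariate. A baseline-outcome correlation of about 0.30 would restore 80% at 28:18. The documents give no correlation and Table 4 claims no such gain, so this is possible but not shown. Dropout works the other way: losing 5% of a 28:18 sample would bring unadjusted power to about 74%.

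A reader might infer three stronger things, which the documents do not support:

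- That the unequal FAAH split explains the whole shortfall. On the t-test reading about half comes from the 24-per-group label, which lowers CNR1 too.
- That the allele-frequency basis claimed in the feasibility paragraph is false for FAAH. A frequency of 0.25 gives about 26:20, which is fairly close to an approximate equal split. The clear clash is with the 60:40 sentence.
- That power could fall to 71%. This takes the low end, 0.16, of the NCBI range quoted in the section on candidate polymorphisms. That section goes on to report 25% in the laboratory's own sample, and the Aim 2 rationale repeats 0.25.

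**Conclusion.** The inconsistency is real and small. Table 4 assumes 48 patients where 46 are treated, and an equal FAAH split where 60:40 is predicted. On an unadjusted two-sided t-test at alpha 0.05, with the plan's SDs and no dropout, the printed differences have about 78% power for CNR1 and about 76% for FAAH. The 80% detectable differences are about 2% and 5% larger than printed. On a normal approximation at 23:23, CNR1 is as printed, and FAAH has about 78% power with a detectable difference about 2.4% larger. This does not show that Aim 2 is inadequately sized. It shows that the table should be restated for each gene.

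**What to change.** Replace the single column of Table 4, and its label of 24 per group, with two columns: CNR1 at 23 vs 23 and FAAH at 28 vs 18, using the figures in the table above. Remove the equal-split assumption for FAAH, so that the power basis agrees with the predicted 60:40. State the formula, and that the figures are before covariate adjustment and dropout. If the sponsor confirms a normal approximation at 23:23, the printed figures stand for CNR1, and FAAH becomes 48.2 mL, 93.9 mL, 25.2 min, 279 mL and 339 mL. Have the Aim 2 feasibility paragraph refer to these per-gene figures. A range for lower FAAH allele frequencies is optional.

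The cost is a change to one table and a few sentences. The stated sensitivity becomes slightly less favourable, and no patients are added.
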